11.4 Electrocardiogram

Descriptive statistics for ECG parameters (heart rate, RR interval, PR interval, QRS interval, QT interval, and QTc) and changes from baseline values at each assessment time point to the end of study will be presented by treatment group. The QTc will be calculated using both the Bazett and Fridericia corrections (if the vendor does not provide).

Electrocardiographic parameter values are considered PCS if they meet or exceed the higherlimit PCS criteria listed in Table 11–4. The number and percentage of participants with PCS postbaseline ECG values will be tabulated by treatment group. The percentages will be calculated relative to the number of participants with available baseline values and at least 1 postbaseline assessment. The numerator is the total number of participants with available baseline values and at least 1 PCS postbaseline value. A supportive listing of participants with PCS postbaseline values will be provided, including the PID number, baseline, all postbaseline (including non-PCS) values, and change from baseline.

Parameter	Unit	Higher Limit
QRS interval	msec	≥ 120
QRS interval	msec	>120 and increase from baseline > 25%
PR interval	msec	≥ 230
PR interval	msec	>230 and increase from baseline > 25%
QTc	msec	>480 or increase from baseline > 60
QTc	msec	increase from baseline > 30

 Table 11-4
 Criteria for Potentially Clinically Significant Electrocardiograms

QTc = QT interval corrected for heart rate.

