Based on the effectiveness and safety of targeting the ganglionic plexi of the cardiac autonomic nervous system to attenuate AF, the extensive nonclinical and clinical data with botulinum toxin type A (particularly, with onabotulinumtoxinA) administration for multiple indications and into different organ systems, and a sound mechanism for temporary neuromodulation in cardiac surgery patients, Allergan is developing a novel botulinum toxin type A intervention (AGN-151607) for the prevention of POAF to be administered during open-chest cardiac surgery.

AGN-151607 is a highly purified and animal- and human-product-free formulation of botulinum toxin type A. The mechanism of action of AGN-151607 is

Botulinum

neurotoxins exert their effect on cholinergic motor nerve terminals through a sequential process: 1) binding to presynaptic cholinergic motor axon terminals, 2) internalization or entry into the nerve terminal, and 3) exertion of the pharmacologic action (ie, inhibition of acetylcholine release) within the nerve terminal; these processes have been documented for several types of nerves, including autonomic nerves, and are relevant for neuromodulation in autonomic epicardial targets.

AGN-151607

Allergan designed this development program based on the problematic nature of POAF in patients, a long-standing unmet need (the paucity of safe and effective therapies), the encouraging results from nonclinical and initial clinical studies demonstrating temporary neuromodulation with botulinum toxin type A in open-chest cardiac surgery patients, and the general safety of botulinum toxin type A across multiple organs and patient types. If this development program demonstrates efficacy of AGN-151607, combined with an acceptable safety profile, then this will be the first effective, preventive treatment for POAF in more than 20 years and could thus reduce the clinical burden observed in these cardiac surgery patients.

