# 5.2. Exclusion Criteria

Participants are excluded from the study if any of the following criteria apply:

1.	Medical Conditions
1.01	Any uncontrolled clinically significant medical condition other than the one under study that, in the investigator's opinion, would put the participant at an unacceptable risk with exposure to botulinum toxin type A.
1.02	Any medical condition that may put the participant at increased risk with exposure to botulinum toxin type A, including diagnosed muscular dystrophy (eg, Duchenne's muscular dystrophy), myasthenia gravis, Eaton-Lambert syndrome, amyotrophic lateral sclerosis, mitochondrial disease, or any other significant disease which might interfere with neuromuscular function.
1.03	Participants with presence or history of any of the following within 3 months prior to the Day 1 visit that may indicate a vulnerable respiratory state per the investigator's clinical judgment: aspiration pneumonia, lower respiratory tract infections, uncontrolled asthma, severe chronic obstructive pulmonary disease, or otherwise compromised respiratory function.
1.04	Permanent/persistent AF
1.05	Has a known allergy or sensitivity to any botulinum toxin type A preparation
1.06	Has a known allergy or sensitivity to medical adhesive (eg, ECG patch adhesive; hydrogel-based adhesive)
1.07	Severe (> 55 mm left atrial diameter) left atrial enlargement
1.08	Left ventricular ejection fraction (LVEF) < 25%
1.09	Presence or history of symptomatic atrioventricular block $> 1^{st}$ degree within the last 30 days (note: presence of a pacemaker is not exclusionary per se)
1.10	Exclusionary valve repair/replacement procedures include:
	
 
Combination of aortic and mitral valve repair/replacement
 
Isolated tricuspid valve repair/replacement
 

2.	Prior/Concomitant Therapy
2.01	Class I or III antiarrhythmic drugs unless proper washout was documented (Section 6.5.1)

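### SAP Table 11-4 does not say which QTc correction its limits use or how AF/flutter and paced ECGs are handled, and the SAP drops the protocol's non-PCS-baseline condition without listing the change

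*SAP*

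**What the plan says.** SAP 11.4 plans summaries of heart rate, RR, PR, QRS, QT and QTc by treatment group. On the correction it says "The QTc will be calculated using both the Bazett and Fridericia corrections", with the qualifier that this applies if the vendor does not provide QTc. Table 11-4 has two QTc rows, ">480 or increase from baseline > 60" and "increase from baseline > 30" (msec), and neither names a correction. Protocol 8.2.3 and 9.4.2.4 also say only QTc, and 9.4.2.4 leaves the criteria to the SAP.

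For QRS and PR, Table 11-4 has one row on level alone (QRS at or above 120 msec, PR at or above 230 msec). A second row for each also requires a relative rise: ">120 and increase from baseline > 25" per cent for QRS and ">230 and increase from baseline > 25" per cent for PR.

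No rule mentions AF, flutter or pacing. SAP 15.1 and 15.2 bring all post-baseline assessments into the PCS determination. The schedule of activities includes a 12-lead ECG after surgery on Day 1, and ECGs continue at the in-hospital visits. Protocol exclusion criterion 1.09 carries the remark "note: presence of a pacemaker is not exclusionary per se".

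Protocol 9.4.2.4 limits both numerator and denominator of the PCS percentage to participants whose baseline value is not PCS. SAP 11.4 requires only that a baseline value exists. SAP section 16, which lists departures from the protocol, does not mention this one.

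**The concern.** The Bazett formula over-corrects as heart rate rises, so it reports a longer QTc when repolarisation has not changed. The first post-operative ECGs are the ones most likely to be taken at a different rate from baseline. They may also be paced or in AF, which is the condition under study. With the correction unnamed, a programmer could apply the limits to Bazett values, Fridericia values or both, and the counts would differ.

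The level-only rows have a related problem. Without the protocol's baseline condition, a participant who entered with a wide QRS, or who is paced throughout, counts as having a PCS QRS although nothing changed.

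The product is injected into epicardial fat pads to act on cardiac nerves. The protocol describes its processes as documented for several nerve types, "including autonomic nerves, and are relevant for neuromodulation in autonomic epicardial targets". This is therefore a table in which a real conduction or repolarisation effect should be visible. A high background of rate and pacing counts would make one harder to see. SAP 12.0 also unblinds sponsor study personnel at the interim lock while follow-up ECGs continue, so the rule is best fixed before that point.

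**Working it through.** The documents give no expected ECG event rate and no heart rates, so there is no figure of the plan's to reproduce. The limits come from Table 11-4. Heart rates and QTcF levels below are assumptions, shown over a range.

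**Formula.** With RR = 60/HR, QTcB = QT/RR^(1/2) and QTcF = QT/RR^(1/3), so QTcB = QTcF × (HR/60)^(1/6). Holding QTcF constant means no true change, so any movement in QTcB is artefact.

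**One case, QTcF 410 msec.**
- At 65 bpm: 410 × (65/60)^(1/6) = 415.5.
- At 100 bpm: 410 × (100/60)^(1/6) = 446.4.
- Difference: 30.9 msec, which meets the > 30 row.
- From 60 bpm, the row is crossed at 60 × (440/410)^6 = about 92 bpm.

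**Rate at which Bazett alone crosses each rise limit, QTcF 420 msec.**

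| Baseline bpm | > 30 row | > 60 limb |
|---|---|---|
| 60 | 91 | 134 |
| 65 | 98 | 143 |
| 70 | 105 | 153 |
| 75 | 112 | 163 |

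The > 480 limb is reached at 60 × (480/QTcF)^6: about 179 bpm for QTcF 400, 134 for 420 and 101 for 440. Across QTcF 400 to 440 and these baselines, the > 60 limb needs about 129 to 169 bpm. Under Fridericia the change is zero by construction in every case. The artefact therefore falls mainly on the > 30 row, and on > 480 only when QTcF is already high.

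**How often this might happen.** Assume baseline rate 66 bpm (SD 9), a mean rise of 15, 20 or 25 bpm (SD 12) and QTcF fixed at 410. By simulation, the > 30 row is then met by about 6%, 13% and 23% of ECGs under Bazett, and the > 480 or > 60 row by about 0%. Percentages of about 17%, 24% and 33% appear only if the change in QTcF is also given an SD of about 12 msec. About 4% then meet the row with no mean rise in rate, so part of the larger figures is ordinary variability. These are rates per ECG. The SAP counts participants with at least one PCS value, which gives higher percentages.

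**QRS and PR, texts side by side.** Take a participant with a stable QRS of 120 msec or more at baseline and afterwards.
- Protocol 9.4.2.4: baseline is PCS, so the participant is in neither numerator nor denominator.
- SAP 11.4, level-only row: counted.
- SAP 11.4, row requiring a rise above 25%: not counted.

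The same holds for a stable PR of 230 msec or more, and for a stable QTc above 480 msec. The dropped condition therefore matters for the level-only criteria and not for the rise criteria.

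**The case against.** The strongest reply is that the SAP already computes Fridericia as well as Bazett. The table specifications are in a separate document that may show the two corrections in separate rows, and a vendor-supplied QTc may already be Fridericia. This stands against any claim that the plan selects Bazett. It does not settle which correction the limits use, because the SAP does not say.

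Second, a reader might infer that rate and pacing artefacts would be reported as drug effects. The documents do not support that. Counts are tabulated by arm, with no causality label, beside a placebo group randomised 1:1:1. Whatever surgery does to rate and pacing raises all arms.

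Third, a reader might infer a false difference between arms of a definite size. That needs a treatment effect on heart rate, and neither document gives one. Neither states that heart rate rises after surgery. The direction is also open: autonomic blockade could raise the rate and less AF could lower it, while the only cardiac term on the SAP's toxin-spread list is bradycardia. The plan does assume AF in 47.8% of placebo and 27.8% of active participants, so rhythm could differ by arm. Those figures refer to any episode over 30 days, however, and not to rhythm on a 12-lead ECG.

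Fourth, other displays help. Heart rate and RR are summarised by arm in the same section, and listings show baseline and all later values. The QRS row with the 25% requirement ignores a stable paced QRS. A tracing in AF has no PR interval, so if read correctly it gives no PR value to flag. The protocol also plans a cardiologist over-read and a display of abnormalities judged clinically significant by the investigator, although SAP 11.4 does not repeat the latter.

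Finally, simply excluding AF and paced ECGs would be a poor remedy. It selects on events after randomisation that treatment may change, and could remove participants paced for new conduction block. That objection stands and shapes the fix.

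**Conclusion.** The point holds as three gaps in SAP 11.4: the correction behind the QTc limits is not named, there is no provision for AF/flutter or paced ECGs, and the protocol's baseline condition is dropped without being listed.

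If Bazett values are used, rate alone meets the > 30 msec row at about 91 to 112 bpm from baselines of 60 to 75 bpm (QTcF 420). The > 60 limb is out of reach below about 134 bpm under the same assumption. A stable QRS of 120 msec or more is counted whichever correction is chosen.

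The expected consequence is extra background in all arms, which can obscure a real effect. Bias between arms would follow only if treatment changes rate, rhythm or pacing, which is plausible but of unknown direction. The documents do not support a claim that Bazett is singled out, that the counts are treated as drug-related, or that a false between-arm difference of any particular size will arise. The table is descriptive and no hypothesis test depends on it. The change is still worth making, because it is cheap and this is a cardiac safety table.

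**What to change.** In SAP 11.4 and Table 11-4:

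1. Apply the QTc limits and the QTc change summaries to Fridericia values as primary, whether the vendor or the sponsor computes them. Keep Bazett as supportive or in listings.
2. Keep all ECGs in the main table. Add rows by arm and visit for the number of ECGs in AF/flutter and the number paced, taken from the planned cardiologist over-read. Show the QRS, PR and QTc counts with and without those ECGs.
3. Restore the non-PCS-baseline condition of protocol 9.4.2.4, stating that it acts on the level criteria (QRS, PR and QTc > 480), or list its removal with a reason in section 16.

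The cost is a wording change and a few more table rows. The over-read is already planned, so no new data collection should be needed.

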### 8.2.3. Electrocardiograms

- Sites or designee shall transmit all study-required ECGs obtained to the ECG vendor. If multiple ECGs have been obtained for the same participant on the same date, the first readable ECG shall be entered as the visit ECG, and all others shall be entered as unscheduled. All readable ECGs received by the vendor shall be sent for ECG vendor, cardiologist over-read. The sponsor will receive all ECG data, including vendor cardiologist assessments, in the data transfer, including those ECGs that could not be evaluated.
- On Visit 2, Day 1, two 12-lead ECGs will be performed; 1 before surgery and 1 after surgery.
- A 12-lead ECG will be obtained in the supine or semi-recumbent position as outlined in the SoA (see Section 1.3) using an ECG machine that automatically calculates the heart rate and measures PR, QRS, QT, and QTc intervals.
- The X-axis speed will be a standard 25 mm per second; the ECG tracing will be kept at the study site. Measurements will be recorded for the following parameters in lead II or lead III: heart rate, PR interval, QRS duration, QT interval, and QTc. All ECGs will be clinically interpreted by the investigator or sub-investigator.

AGN-151607

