#### 9.4.2.4. Electrocardiograms

Descriptive statistics for ECG parameters (heart rate, RR interval, PR interval, QRS interval, QT interval, and QTc) and changes from baseline values at each assessment timepoint to the end of study will be presented by treatment group.

Electrocardiographic parameter values are considered PCS if they meet or exceed the higher-limit PCS criteria. PCS criteria will be specified in the SAP. The number and percentage of participants with PCS postbaseline ECG values will be tabulated by treatment group. The percentages will be calculated relative to the number of participants with available non-PCS baseline values and at least 1 postbaseline assessment. The numerator is the total number of participants with available non-PCS baseline values and at least 1 PCS postbaseline value. A supportive tabular display of participants with PCS postbaseline values will be provided, including the participant number, baseline, all postbaseline (including non-PCS) values, and change from baseline.

A tabular display showing participants with postbaseline clinically significant ECG abnormalities according to the investigator's overall interpretation will be provided.

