15.0 Data Handling Conventions

15.1 Visit Time Windows

Table 15–1 presents the visits assigned for safety analyses and the corresponding range of treatment days (window) during which an actual visit may occur. Unless otherwise specified, efficacy parameters collected by visit (e.g., Quality of Life Outcomes) will use the same windows during which an actual visit may occur. All analyzable ePatch data collected from ePatches with a start date within the visit window will be included in the analysis for the derived visit for Days 60, 90, 180, 270, and 360.

Scheduled Visit	Study Day ^a	Time Window (Study Day Range)
Baseline	1	1
Day 2	2	2
Day 3	3	3
Day 4	4	4
Day 5	5	5
Day 6	6	[6, 10]
Day 14	14	[11, 21]
Day 30	30	[22, 45]
Day 60	60	[46, 75]
Day 90	90	[76, 135]
Day 180	180	[136, 225]
Day 270	270	[226, 315]
Day 360	360	> 315 days

Table 15–1Analysis Visit Windows

a Relative to the date of the study treatment. Day 1 = the date of the study treatment.

If the assessment date (if the assessment date is unavailable, use visit date instead) is on or after the date of the study treatment, the study day is calculated by assessment date – date of the study treatment + 1. If the assessment date is before the date of the study treatment, the study day is calculated by assessment date – date of the study treatment. Therefore, a negative day indicates a day before the start of the study treatment.

If a subject has 2 or more visits within the same window, the last visit with a non-missing value will be used for analysis. All postbaseline assessments will be considered for PCS categorization. All assessments will be included in respective listings.

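### SAP 11.4 drops the protocol's non-PCS baseline condition from the ECG table, so on the threshold-only criteria an unchanged pre-surgery abnormality counts as a post-baseline event

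*SAP*

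**What the plan says.** **Protocol 9.4.2.4.** The denominator is restricted: "The percentages will be calculated relative to the number of participants with available non-PCS baseline values and at least 1 postbaseline assessment". So is the numerator: "The numerator is the total number of participants with available non-PCS baseline values and at least 1 PCS postbaseline value".

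**SAP 11.4.** The same two sentences appear without the restriction. For the denominator: "The percentages will be calculated relative to the number of participants with available baseline values and at least 1 postbaseline assessment". For the numerator: "The numerator is the total number of participants with available baseline values and at least 1 PCS postbaseline value".

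**SAP Table 11-4.** There are six criteria. QRS and PR each have a threshold row (at least 120 msec and at least 230 msec) and a second row that adds a relative increase; for QRS it reads ">120 and increase from baseline > 25" per cent. QTc has a mixed row, ">480 or increase from baseline > 60" msec, and a row for an increase above 30 msec.

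**Elsewhere in the SAP.** Section 11.2 keeps the non-PCS baseline condition in numerator and denominator for laboratory values. Section 16 lists three changes from the protocol (logistic regression dropped, length-of-stay methods, the 6-minute endpoint). Neither it nor the version history in Section 17 mentions the ECG rule.

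**Day 1 readings.** Protocol 8.2.3 says: "On Visit 2, Day 1, two 12-lead ECGs will be performed; 1 before surgery and 1 after surgery". The Schedule of Activities asks for vital signs before and after surgery as well. SAP Table 15-1 assigns study Day 1 only to Baseline, and its first post-baseline window is Day 2.

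**The concern.** The PCS table should show who developed an abnormal ECG after the injection. Without the baseline condition, its threshold rows mix new cases with people who came to surgery already beyond the limit. Such people can enrol: exclusion criterion 1.09 removes only symptomatic atrioventricular block above first degree within the last 30 days, and the trial takes cardiac surgery patients aged 55 to 90. Conduction is a direct safety question for a toxin injected into fat pads that hold cardiac ganglia. A rule that raises the background rate in every arm makes a real effect harder to see. The SAP also departs from the protocol without saying so, and applies one rule to laboratory values and another to ECGs.

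**Working it through.** The documents state no figure for this table, so there is none to reproduce. The check has three steps.

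**1. Which criteria are affected.** Apply each row to an abnormality that does not change from before to after surgery.

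| Parameter, before to after (msec) | Threshold criterion | Change-required criterion | Protocol rule, threshold criterion |
|---|---|---|---|
| QRS 130 to 130 | counted (130 ≥ 120) | not counted (0% increase) | outside numerator and denominator |
| PR 240 to 240 | counted (240 ≥ 230) | not counted (0% increase) | outside both |
| QTc 490 to 490 | counted (490 > 480) | not counted (0 increase) | outside both |

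The effect is confined to the two pure threshold rows and the first half of the mixed QTc row. One reading past the limit at any post-baseline ECG is enough to be counted.

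SAP 11.3 drops the same condition for vital signs, but every criterion in Table 11-3 requires a change from baseline, so an unchanged abnormality is not counted there.

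**2. Size, as an illustration.** Let b be the proportion past the limit at baseline, all of whom stay past it, and r the new-case rate among the rest.

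- Protocol rule: rate = r, on n(1 − b) participants.
- SAP rule: rate = b + (1 − b)r, on n participants.
- The risk difference under the SAP rule is therefore (1 − b) times the difference in r.

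Neither b nor r is in the documents; all values below are assumptions.

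| b | r = 4% vs 8%: SAP shows | Ratio (protocol rule 2.00) | Difference (protocol rule 4.0 points) |
|---|---|---|---|
| 10% | 13.6% vs 17.2% | 1.26 | 3.6 |
| 15% | 18.4% vs 21.8% | 1.18 | 3.4 |
| 20% | 23.2% vs 26.4% | 1.14 | 3.2 |

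For example, 0.15 + 0.85 × 0.04 = 0.184, 0.15 + 0.85 × 0.08 = 0.218, and 0.218 / 0.184 = 1.18. With a larger assumed contrast, 5% vs 15%, the ratio of 3.00 becomes 1.62 at b = 10% (14.5% vs 23.5%) and 1.33 at b = 20% (24.0% vs 32.0%). With b = 0 the two rules agree.

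**3. The Day 1 window.** By the SAP 15.1 formula, an ECG on the date of injection has study day 0 + 1 = 1. In Table 15-1 that day maps only to Baseline. The post-surgery ECG is not a baseline value, because SAP 11.0 and 15.2 define baseline as the last non-missing value before study treatment. It therefore has no row in the by-visit summaries. It still enters the PCS count, since SAP 15.1 and 15.2 use all post-baseline assessments for PCS.

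**The case against.** **In defence of SAP 11.4.** Protocol 9.4.2 leaves full definition of the safety analysis to the SAP. Each QRS and PR threshold row is paired with a row that requires a change, and QTc has a change-only row. The supportive listing shows baseline and all later values, so carried-over cases can be identified. The table is descriptive, and randomization balances baseline abnormality on average. The protocol rule has its own cost, since a participant with an abnormal baseline who worsens is left out of the restricted table.

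Much of this stands, and the last point shapes the fix. It does not remove the problem. Leaving definition to the SAP does not explain an unlisted reversal of a rule that the protocol states. The paired rows do not replace the threshold rows: a QRS going from 110 to 125 msec newly crosses 120, but the rise is 15/110 = 13.6%, so only the threshold row shows it. A listing is no substitute for a correct table.

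**Stronger readings that the documents do not support.**

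- A reader might infer that the post-surgery Day 1 ECG becomes the baseline, because SAP 15.1 says: "If a subject has 2 or more visits within the same window, the last visit with a non-missing value will be used for analysis". SAP 11.0 and 15.2 fix baseline as pre-treatment, and both Day 1 ECGs belong to one visit. Protocol 8.2.3 makes the first readable ECG of a date the visit ECG and the others unscheduled.
- A reader might infer that this ECG is lost from the PCS table. It is not, as shown above.
- A reader might infer that everyone with a pacemaker or bundle-branch block is counted as an event. Criterion 1.09 says only that a pacemaker does not by itself exclude. A participant is counted only if the measured interval passes a limit.
- A reader might infer a systematic bias between arms. With baseline prevalence balanced on average, the effect is inflation and dilution.

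**Conclusion.** The departure from the protocol is plain on the page and is not listed. Its direction is also certain: for any baseline abnormality that persists, the threshold rows overstate absolute rates and pull a real dose-placebo contrast toward no difference.

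The size is not known. The illustration rests on assumed prevalences and new-case rates and on full persistence. The ratio shrinks far more than the risk difference, which falls only from 4.0 to between 3.2 and 3.6 points in the first example.

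The reach is limited to QRS at least 120, PR at least 230 and the above-480 part of QTc. The point should be corrected, but it concerns a descriptive safety table and does not touch the efficacy analyses.

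The Day 1 matter is minor: one missing row in the by-visit ECG and vital sign summaries. The separate table specifications, which are not among these documents, may already provide it. Day 2 (Visit 3) has its own window.

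**What to change.** 1. In SAP 11.4, restore the non-PCS baseline condition in numerator and denominator for QRS at least 120 and PR at least 230, and state that it is applied criterion by criterion.
2. Split the mixed QTc row in two: above 480, restricted to participants with a non-PCS baseline; and increase above 60, for all participants with a baseline value.
3. Keep all participants with a baseline value on the rows that require a change, so that worsening from an abnormal baseline is still seen. Record in Section 16 whatever then differs from Protocol 9.4.2.4.
4. Minor: add a Day 1 post-surgery analysis visit to Table 15-1 for ECG and vital signs, and state there that the Baseline row is pre-injection only, as SAP 11.0 and 15.2 already define it.

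The cost is SAP wording and table shells, with no new data. The downside is somewhat smaller denominators on the threshold rows. With about 330 / 3 = 110 participants per arm, an assumed 10% abnormal at baseline leaves 110 × 0.90 = 99, and 20% leaves 110 × 0.80 = 88.
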